4.2. Scientific Rationale for Study Design

In preclinical in vitro inhibition studies, the potential for PF-04965842 to inhibit MATE1 and MATE2K was assessed. A steady-state total C_{max} of PF-04965842 was 3.7 μ M (1199 ng/mL) at a maximum clinical dose of 200 mg daily and unbound C_{max}/IC_{50} ratio is 0.24 and 0.13 for MATE1 and MATE2K, respectively, suggesting that PF-04965842 has a potential to inhibit these drug transporters in vivo as ratios exceed the in vitro regulatory threshold unbound C_{max}/IC_{50} ratio of 0.02.⁸

Therefore, a clinical interaction study with a sensitive MATE1 and MATE2K substrate is needed to assess the effect of PF-04965842 on the activity of these transporters. The primary purpose of this study is to assess the effect of PF-04965842 on the in vivo pharmacokinetics (PK) of metformin, a sensitive substrate for MATE1 and MATE2K.⁸ Metformin is also a substrate for organic cation transporter (OCT)1 and OCT2 however PF-04965842 is not an inhibitor of OCT2 (C_{max}/IC_{50} ratio is >300) and despite the unbound PF-04965842 C_{max}/IC_{50} ratio for OCT1 is just above 0.02 (0.03), inhibition of OCT1, a hepatic uptake transporter, is not expected to increase plasma metformin exposures as OCT1 does not modulate metformin clearance as it is primarily excreted unchanged in urine. Both MATE1 and MATE2K are renal transporters that are expressed in the apical membrane of the renal proximal tubules thus play an important role in tubular secretion and reabsorption of drug molecules in the kidney. Therefore, significant MATE1/2K inhibition would primarily impact the renal clearance of substrates for these transporters with having minimal effects, if any, on plasma exposures.

NMN, a metabolite of niacin, has been reported to be an endogenous biomarker for assessing MATE/OCT2 inhibition. Renal clearance of NMN was shown to be reduced by ~70% by pyrimethamine, a potent MATE/OCT2 inhibitor.⁹ As such, NMN is being assessed in this study to further investigate the utility of this endogenous substance as a biomarker for MATE

activity in comparison to metform in, the gold standard for assessing MATE activity in DDI studies.⁸

Preliminary SimCYP[®] modelling of PF-04965842 dosed at 200 mg QD indicated a low risk of precipitating a significant drug interaction with metformin, a MATE1 and MATE2K substrate. Additionally, PF-04965842 did not significantly affect 24 hour urinary creatinine (a MATE1/2K and OCT2 substrate) up to doses of 800 mg in clinical studies.

Banked biospecimens will be collected for exploratory

pharmacogenomic/genomic/biomarker analyses and retained in the Biospecimen Banking System (BBS), which makes it possible to better understand the investigational product's mechanism of action and to seek explanations for differences in, for example, exposure, tolerability, safety, and/or efficacy not anticipated prior to the beginning of the study.

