Preclinical in vitro inhibition studies showed that the unbound maximum observed concentration $(C_{max})/50\%$ inhibitory concentration (IC50) ratio is 0.24 and 0.13 for multidrug and toxic compound extrusion transporter (MATE)1 and MATE2K, respectively, suggesting that PF-04965842 has a potential to inhibit these drug transporters in vivo as ratios exceed the in vitro regulatory threshold unbound C_{max}/IC_{50} ratio of 0.02.⁸ Therefore, a clinical interaction study with a sensitive MATE1 and MATE2K substrate is needed to assess the effect of PF-04965842 on the activity of these transporters. The primary purpose of this study is to assess the effect of PF-04965842 on the in vivo pharmacokinetics (PK) of metformin, a sensitive substrate for MATE1 and MATE2K.⁸ Metformin is also a substrate for organic cation transporter (OCT)1 and OCT2. However, PF-04965842 is not an inhibitor of OCT2 (C_{max}/IC50 ratio is >300) and despite the unbound PF-04965842 C_{max}/IC50 ratio for OCT1 being just above 0.02 (0.03), inhibition of OCT1, a hepatic uptake transporter, is not expected to increase plasma metformin exposures as OCT1 does not modulate metformin clearance as it is primarily excreted unchanged in urine. Both MATE1 and MATE2K are renal transporters that are expressed in the apical membrane of the renal proximal tubules thus play an important role in tubular secretion and reabsorption of drug molecules in the kidney. Therefore, significant MATE1/2K inhibition would primarily impact the renal clearance of substrates for these transporters with having minimal effects, if any, on plasma exposures.

 N^{1} -methylnicotinamide (NMN), a metabolite of niacin, has been reported to be an endogenous biomarker for assessing MATE/OCT2 inhibition. Renal clearance of NMN was shown to be reduced by ~70% by pyrimethamine, a potent MATE/OCT2 inhibitor.⁹ As such, NMN is being assessed in this study to further investigate the utility of this endogenous substance as a biomarker for MATE activity in comparison to metformin, the gold standard for assessing MATE activity in drug-drug interaction (DDI) studies.⁸

Objectives and Endpoints

Objectives:	Endpoints:
Primary:	Primary:
• To estimate the effect of PF-04965842 on MATE1/2K activity via the pharmacokinetic assessment of a single, oral dose of metformin in healthy participants.	Metformin CL _{r.}
Secondary:	Secondary:

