2.2.4.1. Summary of Safety Data from Completed Studies

Based on the clinical experience with PF-04965842 and its mechanism of action, the potential risks of treatment with JAK inhibitors include: (1) viral reactivation; (2) serious infection and opportunistic infections; (3) malignancy and lymphoproliferative disorders; (4) decreased lymphocyte counts; (5) decreased neutrophil counts; (6) decreased platelets; and (7) alterations in the lipid profile.

In the completed Phase 1 and 2 studies in healthy participants, participants with psoriasis and participants with AD, PF-04965842 was generally safe and well tolerated.

In the completed Phase 1 studies in healthy participants receiving single doses of PF-04965842 up to 800 mg and multiple doses up to 200 mg twice daily (BID) or 400 mg once daily (QD), the most commonly reported adverse events (AEs) were diarrhea, nausea, vomiting, headache, acne, and dizziness. Following single or multiple dose of PF-04965842, most reported treatment emergent AEs (TEAEs) were mild or moderate in severity. In study B7451001, during the single-ascending dose phase, 1 participant in the placebo group had maximum QT interval calculated using Fridericia's correction factor (QTcF) interval of 450-<480 msec, and 1 participant in the PF-04965842 800 mg treatment group had maximum QTcF interval increase from baseline of 30 to <60 msec. In the multiple-ascending dose phase, 3 participants (1 each in the placebo, PF-04965842 30 mg QD, and 100 mg QD treatment groups) had maximum QTcF interval of 450-<480 msec, and 2 participants in the PF-04965842 200 mg BID treatment group had maximum QTcF interval increase from baseline of 30 to <60 msec.

In the completed Phase 2 study in participants with moderate to severe psoriasis (B7451005), the most frequently reported AEs across the PF-04965842 treatment groups (200 mg BID, 200 mg QD, and 400 mg QD) were nausea, followed by headache. Other commonly reported AEs include neutropenia and neutrophil counts decreased, thrombocytopenia and platelet count decreased. One of the participants in the 200 mg QD group with an AE categorized as infections and infestations was reported as having VIIth nerve paralysis

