4.3. Justification for Dose

An oral dose of 200 mg QD PF-04965842 and a single oral dose of metformin 500 mg will be used in this study.

An oral dose of 200 mg QD PF-04965842 for 2 days will be used as it is the highest dose and administration frequency being evaluated in the Phase 3 AD program. Drug concentration accumulation of PF-04965842 is minimal after repeated oral administration at doses lower than 200 mg BID, consistent with the prediction from the short half-life. PF-04965842 also displays linear PK at the 200 mg dose with no evidence of mechanism-based inhibition. Oral doses of PF-04965842 as high as 800 mg (single dose), 400 mg QD and 200 mg BID (up to 10 days) have been found to be safe and well tolerated. Based on the safety data of PF-04965842 and prior clinical experience as described above, administration of PF-04965842 200 mg QD for 2 days is expected to pose little risk to healthy adult participants.

Metformin is approved to improve glycemic control in adults and pediatric patients 10 years of age and older with type 2 diabetes mellitus. An oral dose of 500 mg of metformin will be used in this study as this is the lowest approved single dose used in clinical practice and will provide metformin exposures at the lower end of clinically-relevant metformin doses in the even that metformin exposures are increased in the presence of PF-04965842. The most common adverse reactions (>5.0%) in clinical studies following multiple dose administration of metformin were diarrhea, nausea/vomiting, flatulence, asthenia, indigestion, abdominal discomfort, and headache with the risk of adverse events likely to be lower with a single dose administration. Thus, a single 500 mg dose of metformin is anticipated to be safe and generally well-tolerated in healthy participants.

The absolute bioavailability of a metformin 500 mg tablet given under fasting conditions is approximately 50% to 60%. After oral administration of a single 500 mg dose of metformin in healthy participants, C_{max} occurs at approximately 3 hour post administration in the fasted state. Studies using single oral doses of metformin 500 to 1500 mg and 850 to 2550 mg, indicate that there is a lack of dose proportionality with increasing doses, which is due to decreased absorption rather than an alteration in elimination. Intravenous single-dose studies

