in normal subjects demonstrate that metformin is excreted unchanged in the urine and does not undergo hepatic metabolism (no metabolites have been identified in humans) nor biliary excretion. Renal clearance is approximately 3.5 times greater than creatinine clearance, which indicates that tubular secretion is the major route of metformin elimination. Following oral administration, approximately 90% of the absorbed drug is eliminated via the renal route within the first 24 hours, with a plasma elimination half-life of approximately 6.2 hours. In blood, the elimination half-life is approximately 17.6 hours, suggesting that the erythrocyte mass may be a compartment of distribution.^{14, 15}

Metformin will be administered following consumption of a moderate fat meal as metformin is administered with food, in standard clinical practice, to improve its tolerability. Food decreases the extent of absorption of metformin and slightly delays its absorption, as shown by an approximate 40% lower mean C_{max} , 25% lower AUC, and a 35-minute prolongation of T_{max} following administration of a single 850 mg tablet of metformin with food, compared to the same tablet strength administered fasting.^{14, 15} Administration of 4 × 100 mg PF-04965842 tablets (400 mg) with food did not change AUC_{inf}, and appeared to result in slightly lower C_{max} with reduced variability compared to fasted conditions. As such, PF-04965842 will also be administered with a moderate fat meal during co-administration with metformin and can be administered with or without food when dosed on Day 2.

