9.4.4.2. Derivation of Pharmacokinetic Parameters Prior to Analysis

PK parameters for metformin and NMN will be derived from the plasma concentration-time profiles and urine concentrations as shown below in Table 6.

Parameter	Definition	Method of Determination	Analyte
AUC ₂₄	Area under the plasma concentration-time profile from time zero to 24 hours	Linear/Log trapezoidal method.	N
AUC _{last}	Area under the plasma concentration-time profile from time zero to the time of the last quantifiable concentration (C_{last})	Linear/Log trapezoidal method.	N, M
AUC _{inf} ^a	Area under the plasma concentration-time profile from time zero extrapolated to infinity	$AUC_{last} + (C_{last}*/k_{el}),$ where $C_{last}*$ is the predicted plasma concentration at the last quantifiable time point estimated from the log-linear regression analysis.	Μ
C _{max} T _{max}	Maximum plasma concentration Time for C_{max}	Observed directly from data. Observed directly from data as time of first occurrence.	N, M N, M
$\mathbf{t}_{1_2}^{'}$	Terminal elimination half-life	$Log_e(2)/k_{el}$, where k_{el} is the terminal phase rate constant calculated by a linear regression of the log-linear concentration-time curve. Only those data points judged to describe the terminal log-linear decline will be used in the regression.	Μ
CL/F	Apparent clearance for extravascular dosing	Dose/AUC _{inf.}	М
V/F	Apparent volume of distribution for extravascular dosing	Apparent volume of distribution, estimated from terminal phase, for extravascular dosing.	М
Ae	Cumulative amount of drug recovered unchanged in urine	Sum of amount excreted for each collection period (Urine Concentration * Volume of Urine).	N, M
Ae%	Cumulative amount of drug recovered unchanged in urine, expressed as percent of dose	$100 \times (Ae/Dose).$	М
		Ae/AUC.	

Table 6.Derivation of PK Parameters

Actual PK sampling times will be used in the derivation of PK parameters.

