7.3. Pharmacokinetic Parameters

Actual PK sampling times will be used in the derivation of PK parameters.

If a PK parameter cannot be derived from a subject's concentration data, the parameter will be coded as NC (ie, not calculated). (Note that NC values will not be generated beyond the day that a subject discontinues).

In summary tables, statistics will be calculated by setting NC values to missing; and statistics will be presented for a particular treatment with ≥ 3 evaluable measurements. For statistical analyses (ie, analysis of variance), PK parameters coded as NC will also be set to missing; and analyses will not be performed for a particular parameter if more than 50% of the data are NC.

If an individual subject has a known biased estimate of a PK parameter (due for example to an unexpected event such as vomiting before all the compound is adequately absorbed in the body), this will be footnoted in summary tables and will not be included in the calculation of summary statistics or statistical analyses.

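### Does the protocol's remark that MATE inhibition barely affects plasma exposure leave a fall in metformin renal clearance open to misreading?

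*Protocol*

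**What the plan says.** The rationale in Protocol 1.1 and 4.2 ends with the statement that significant MATE1/2K inhibition "would primarily impact the renal clearance of substrates for these transporters with having minimal effects, if any, on plasma exposures".

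Protocol 4.3 describes metformin's elimination. It says that "metformin is excreted unchanged in the urine and does not undergo hepatic metabolism", rules out biliary excretion, and adds that "approximately 90% of the absorbed drug is eliminated via the renal route within the first 24 hours". It also justifies the metformin dose with an eye to the event that "metformin exposures are increased in the presence of PF-04965842".

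Metformin CLr is the only primary endpoint (Protocol 3). In Table 6 (Protocol 9.4.4.2) CLr is Ae divided by AUC, and Ae is the "Sum of amount excreted for each collection period". Metformin AUCinf is analysed in the same mixed model as CLr. Ae, Ae% and CL/F are summarised by treatment (SAP 6.3.1 and 8.2). Table 4 tabulates precision for CLr ratios of 60-100% and AUCinf ratios of 100-200%. SAP 4.2 states that there are no decision rules.

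On faulty data, SAP 7.3 drops a parameter when a participant "has a known biased estimate of a PK parameter (due for example to an unexpected event such as vomiting", and SAP 5.6 and 5.6.2 provide for review of deviations and exclusion from the PK analysis.

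**The concern.** If nearly all absorbed metformin leaves through the kidney, renal clearance is nearly total clearance, and it cannot fall clearly while AUC stays flat. The rationale says otherwise.

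This could matter because Ae is a sum over collection intervals. A lost void lowers Ae and hence CLr but leaves plasma AUC unchanged. A fall in CLr with flat AUC is therefore what incomplete urine produces, and it is also what the rationale tells the reader to expect from true inhibition. With no decision rule, the primary result is interpreted by judgement, and no text says that CLr is to be read against AUCinf and Ae.

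A treatment-related loss can be imagined. In the sponsor's healthy-participant studies "the most commonly reported adverse events (AEs) were diarrhea, nausea, vomiting, headache, acne, and dizziness", Protocol 4.3 lists diarrhea for metformin as well, and only Treatment B gives both drugs. The worry is that a collection artefact could be reported as transporter inhibition.

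**Working it through.** **1. Reproduce the planned precision.** Inputs from Protocol 9.2: n = 12, within-participant SD 0.156 (AUCinf) and 0.173 (CLr), 80% assurance. The 2x2 crossover has 10 degrees of freedom.

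Half-width = t(0.95, 10) × SD × √(2/12) × √(χ²(0.80, 10)/10), with t = 1.8125 and χ² = 13.442.

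- AUCinf: 1.8125 × 0.156 × 0.4082 × 1.1594 = 0.1338 (stated 0.134)
- CLr: 1.8125 × 0.173 × 0.4082 × 1.1594 = 0.1484 (stated 0.148)

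The plan's figures reproduce.

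**2. AUC implied by a fall in CLr.** Let R be the CLr ratio and f the renal fraction of clearance. With bioavailability and non-renal clearance unchanged (an assumption), AUCinf ratio = 1/(1 − f(1 − R)). Protocol 4.3 supports f of 0.9 to 1.0. The Ae(0-48 h) column also assumes one compartment and the 6.2-hour half-life in 4.3.

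| CLr ratio | AUCinf ratio, f = 0.9 to 1.0 | Ae(0-48 h) ratio |
|---|---|---|
| 90% | 110-111% | 0.986-0.997 |
| 80% | 122-125% | 0.968-0.991 |
| 70% | 137-143% | 0.944-0.981 |
| 60% | 156-167% | 0.912-0.965 |

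So the clause is wrong for metformin when the effect is large. These rows are Table 4 planning scenarios, not predictions.

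**3. Where flat AUC argues against inhibition.** The planned AUCinf interval lies above 100% only if the ratio exceeds exp(0.1338) = 1.143. That needs R ≤ 1 − (1 − 1/1.143)/f, which is 0.861 at f = 0.9 and 0.875 at f = 1.0. For smaller effects, flat AUC is compatible with true inhibition.

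The documents point to that region. Protocol 4.2 gives an unbound Cmax/IC50 of 0.24 for MATE1, and 4.3 puts CLr at 3.5 times creatinine clearance, so secretion is about 1 − 1/3.5 = 71% of CLr. If all secretion ran through MATE1 and inhibition stayed at its peak (both assumptions), R = 0.286 + 0.714/1.24 = 0.86.

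**4. How much urine loss would mislead.** Loss rates here are assumptions; the documents give none.

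- No drug effect, uniform Test-period loss: the CLr interval excludes 100% once loss reaches 1 − exp(−0.1484) = 13.8%.
- No drug effect, two of 12 losing 30%: ratio 0.7^(2/12) = 0.94, interval about 81-109%, which includes 100%.
- True CLr 90%, 5% uniform loss: 0.90 × 0.95 = 85.5%, interval 73.7-99.2%. This excludes 100%, but inhibition is real and the direction is correct.

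**5. Would a written cross-check help?** Take the natural rule: a CLr fall with flat AUCinf and an Ae ratio below about 0.9 prompts a review of urine collection.

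- True CLr 90%, 5% loss: Ae ratio 0.95 × (0.986 to 0.997) = 0.94-0.95. Not expected to fire.
- Two of 12 losing 30%: Ae ratio 0.94. Not expected to fire.
- True CLr 80% at f = 1.0, with absorption 20% lower under Test: AUC = 1.25 × 0.80 = 100% and Ae about 80%. It fires although the urine is complete and inhibition is real.
- Urine lost in the Reference period raises the Test/Reference CLr ratio and hides inhibition. The rule does not look there.

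**The case for a change.** The strongest case for acting is that the conflict is plain, appears twice, and concerns the reading of the only primary endpoint. Section 4.2 itself relies on mainly renal excretion to dismiss OCT1, then denies the consequence. Small losses also shift the odds. At SD 0.173, a uniform 5% Test-period loss raises the chance that the CLr interval lies wholly below 100% from 5% to about 17% with no drug effect, and from about 40% to 66% at a true CLr of 90%. SAP 7.3 acts only on bias already known, and its example is vomiting. A sentence settled before results are seen would cost little.

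The textual conflict stands, and so does the arithmetic. The step to a change in the analysis does not:

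- **The remark directs nothing.** Dose justification, Table 4 and the modelled AUCinf already provide for raised exposure, and Ae and Ae% will be summarised in the same report as CLr. An analyst who sees CLr fall will look at them.
- **The loss is supposed, not shown.** Participants stay in the unit throughout, every void is collected by interval with its volume recorded, and sample-handling deviations must be reported (Protocol 4.1 and 8.5.2). The adverse-event text pools single doses up to 800 mg and multiple doses up to 400 mg daily, and does not mention lost urine.
- **The rule in SAP 7.3 is open-ended.** Vomiting is offered as an example, so a recorded missed void already falls within it.
- **A one-sided trigger brings its own bias.** In a sponsor-open study, re-examining only apparent inhibition would push the primary estimate toward no effect.

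**Conclusion.** No change to the plan follows. The sentence in 1.1 and 4.2 is a slip in background text. On the elimination facts in 4.3, CLr of 80% and 60% would go with AUCinf of about 122-125% and 156-167%. That rests on unchanged bioavailability and non-renal clearance and a renal fraction of 0.9 to 1.0; at a fraction of 0.8 the figures are 119% and 147%, and the point is the same. Correcting the sentence would alter no endpoint, estimate, interval or sample size.

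The silence on reading CLr beside AUCinf and Ae is a gap that analysts fill sensibly, because all three are derived and reported. Incomplete urine is dealt with by full collection under confinement, deviation review and the existing bias rule. With no drug effect, a spurious exclusion of 100% at the planned precision needs about 14% uniform loss confined to Test periods, and nothing in the documents suggests that. The obvious prespecified trigger would not be expected to fire for the smaller losses examined, could flag true inhibition, and would ignore Reference-period loss.

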4.3. Justification for Dose

An oral dose of 200 mg QD PF-04965842 and a single oral dose of metformin 500 mg will be used in this study.

An oral dose of 200 mg QD PF-04965842 for 2 days will be used as it is the highest dose and administration frequency being evaluated in the Phase 3 AD program. Drug concentration accumulation of PF-04965842 is minimal after repeated oral administration at doses lower than 200 mg BID, consistent with the prediction from the short half-life. PF-04965842 also displays linear PK at the 200 mg dose with no evidence of mechanism-based inhibition. Oral doses of PF-04965842 as high as 800 mg (single dose), 400 mg QD and 200 mg BID (up to 10 days) have been found to be safe and well tolerated. Based on the safety data of PF-04965842 and prior clinical experience as described above, administration of PF-04965842 200 mg QD for 2 days is expected to pose little risk to healthy adult participants.

Metformin is approved to improve glycemic control in adults and pediatric patients 10 years of age and older with type 2 diabetes mellitus. An oral dose of 500 mg of metformin will be used in this study as this is the lowest approved single dose used in clinical practice and will provide metformin exposures at the lower end of clinically-relevant metformin doses in the even that metformin exposures are increased in the presence of PF-04965842. The most common adverse reactions (>5.0%) in clinical studies following multiple dose administration of metformin were diarrhea, nausea/vomiting, flatulence, asthenia, indigestion, abdominal discomfort, and headache with the risk of adverse events likely to be lower with a single dose administration. Thus, a single 500 mg dose of metformin is anticipated to be safe and generally well-tolerated in healthy participants.

The absolute bioavailability of a metformin 500 mg tablet given under fasting conditions is approximately 50% to 60%. After oral administration of a single 500 mg dose of metformin in healthy participants, C_{max} occurs at approximately 3 hour post administration in the fasted state. Studies using single oral doses of metformin 500 to 1500 mg and 850 to 2550 mg, indicate that there is a lack of dose proportionality with increasing doses, which is due to decreased absorption rather than an alteration in elimination. Intravenous single-dose studies

in normal subjects demonstrate that metformin is excreted unchanged in the urine and does not undergo hepatic metabolism (no metabolites have been identified in humans) nor biliary excretion. Renal clearance is approximately 3.5 times greater than creatinine clearance, which indicates that tubular secretion is the major route of metformin elimination. Following oral administration, approximately 90% of the absorbed drug is eliminated via the renal route within the first 24 hours, with a plasma elimination half-life of approximately 6.2 hours. In blood, the elimination half-life is approximately 17.6 hours, suggesting that the erythrocyte mass may be a compartment of distribution.^{14, 15}

Metformin will be administered following consumption of a moderate fat meal as metformin is administered with food, in standard clinical practice, to improve its tolerability. Food decreases the extent of absorption of metformin and slightly delays its absorption, as shown by an approximate 40% lower mean C_{max} , 25% lower AUC, and a 35-minute prolongation of T_{max} following administration of a single 850 mg tablet of metformin with food, compared to the same tablet strength administered fasting.^{14, 15} Administration of 4 × 100 mg PF-04965842 tablets (400 mg) with food did not change AUC_{inf}, and appeared to result in slightly lower C_{max} with reduced variability compared to fasted conditions. As such, PF-04965842 will also be administered with a moderate fat meal during co-administration with metformin and can be administered with or without food when dosed on Day 2.

